3.1 Objectives and Endpoints

Objectives	Endpoints			
 Primary objective To assess the efficacy of zabedosertib vs. placebo in adult patients with moderate-to-severe atopic dermatitis (AD) with inadequate response to topical corticosteroids or if topical treatments are medically not advisable 	 Primary endpoint: Achievement of 75% reduction from baseline in the Eczema Area and Severity Index (EASI 75 response) at Week 12 (Day 84) Primary endpoint (see Section 3.2) is the composite variable defined as follows: an EASI 75 response at Week 12 (Day 84), no stop of study intervention for reasons related to lack of efficacy, no rescue medication use during the 4 weeks before Day 84 and no use of systemic AD treatment. 			
	 Secondary endpoints: Percent change from baseline in EASI at Week 12 (Day 84) Achievement of EASI 50 response at Week 12 (Day 84) Achievement of EASI 90 response at Week 12 (Day 84) Achievement of a vIGA-AD response (score 0 or 1 and ≥ 2 points improvement) at Week 12 (Day 84) Absolute change from baseline in body surface area (BSA) affected by AD at Week 12 (Day 84) Absolute values and percent change of the weekly average of the Peak Pruritus 0-10 NRS score from baseline at Week 12 (Day 84) Achievement of a ≥ 4 point-improvement (reduction) in the weekly average of the Peak Pruritus 0-10 NRS score from baseline at Week 12 (Day 84) for participants with Peak Pruritus 0-10 NRS score ≥ 4 at baseline 			

Clinical Study Protocol Amendment 1 BAY 1834845 / 22158

Page: 24 of 93

Objectives	Endpoints
Secondary objectives	
 To assess the safety and tolerability of zabedosertib vs. placebo 	 Secondary endpoints: Frequency and severity of TEAEs Other safety endpoints: Frequency and severity of TEAEs of special interest Changes in vital signs from baseline Changes in clinical laboratory test results from baseline (e.g., chemistry lipid panel, hematology, urinalyses) Changes in ECG parameters from baseline and frequency of ECG findings
Other pre-specified / Exploratory objectives	Other Pre-Specified Endpoints
• To further assess the efficacy of zabedosertib vs. placebo	 Achievement of EASI 75 response up to Week 8 (Day 56) Achievement of EASI 100 response at Week 12 (Day 84) Achievement of a ≥ 3 point- improvement (reduction) in the weekly average of the Peak Pruritus 0-10 NRS from baseline at Week 12 (Day 84)
	 Absolute values and percent change from baseline in weekly averages of Peak Pruritus 0-10 NRS scores over time

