- 4. Any clinically relevant abnormal findings in medical condition or history thereof or any deviation from normal laboratory values, physical examination, vital signs, 12-lead ECG at screening or randomization which in the opinion of the investigator, may put the participant at risk by participation in the study or provide difficulties in interpreting the trial data.
- 5. Participants with any of the following within 12 weeks of study entry: myocardial infarction, unstable ischemic heart disease or cerebrovascular accident.
- 6. Current or history of lymphoproliferative disease; or signs or symptoms suggestive of possible lymphoproliferative disease, including lymphadenopathy or splenomegaly; or active primary or recurrent malignant disease; or been in remission from clinically significant malignancy for < 5 years.

The following exceptions to the above are acceptable for enrollment:

- a. Cervical carcinoma *in situ* that has been resected with no evidence of recurrence or metastatic disease for \geq 3 years and
- b. Basal cell or squamous epithelial skin cancers that have been completely resected with no evidence of recurrence for ≥ 3 years.
- 7. Known immunodeficiency disorder or immunocompromised state or, in the opinion of the investigator, unacceptable risk for participating in the study.

Prior/Concomitant Therapy

- 8. Use of topical or systemic antihistamines within 7 days before Visit 3
- 9. Use of topical treatments for AD (i.e., topical glucocorticosteroids [TCSs] or topical calcineurin-inhibitors [TCIs] or topical JAK inhibitors) within 7 days before the randomization visit.
- 10. Start use of prescription emollients / moisturizers or emollients / moisturizers containing additives such as urea, ceramides, hyaluronic acid, heparinoid or any other active substances during the screening period or during the study.
- 11. Systemic immunosuppressive/ immunomodulating therapy (e.g., systemic glucocorticoids, cyclosporine, mycophenolate mofetil [MMF], methotrexate, azathioprine or oral Janus kinase (JAK)-inhibiting agents) or phototherapy within 4 weeks before the randomization visit. A stable daily dose of max. 1200 µg inhalative glucocorticosteroid (budesonide or equivalent) is allowed; this includes 'reliever treatment' expected to be required by the patient during the study.

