6.9.2 Rescue Medication

In the event of a disease flare or AD symptoms defined as any worsening of AD to an vIGA \geq 3 requiring escalation of treatment confirmed by an investigator, which cannot be tolerated by the study participant, topical rescue medication as defined below may be used for a timeframe of several days at the discretion of the investigator. Before topical treatment for AD (= rescue medication) is initiated, the frequency of emollient use should be increased to try to control AD symptoms and efficacy assessments should be performed (see below and Section 8.1 [Unscheduled visit]).

Defined rescue medication for this study is the methylprednisolone aceponate (Advantan[®] cream). Only if Advantan cream is not available in the respective country, an alternative TCS with similar potency may be used (see WHO definition for potent corticosteroids group III, such as betamethasone, fluclorolone, desoximetasone, fluocinolone acetonide, budesonide, mometasone, beclomethasone, hydrocortisone aceponate). If TCSs are not tolerated or their use is not advisable, the topical TCIs pimecrolimus 1% (Elidel[®] cream) or tacrolimus (Protopic[®] 0.1% or 0.03% ointment) may be used.

The rescue medication is considered an auxiliary medicinal product (not an investigational product). The daily amount and frequency of application should be once daily for 1 week. If necessary, the duration of application may be extended to a maximum of 2 weeks. The use of rescue medication has to be documented in the CRF, providing information on product, dose, frequency and duration of therapy.

Topical rescue medication will be locally supplied/reimbursed by the sponsor during the study, including follow-up, according to the locally agreed process. Whenever possible, the efficacy assessments using the EASI, vIGA-AD and BSA affected by AD should be performed immediately before start of topical rescue therapy and at its end. Site visits

(scheduled or unscheduled) are therefore strongly recommended before start of rescue treatment.

If topical rescue medication is used, study intervention (zabedosertib or placebo) will be continued and study visits performed according to the SoA (see Section 1.3).

6.9.3 **Prohibited Medication and Therapies**

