Prior and concomitant therapies not permitted in this study are listed in Section 5.2, exclusion criteria. Therapies listed in the exclusion criteria are also prohibited during the study (exception: TCSs and TCIs may only be used as rescue medication).

In addition, the use of antihistamines and live vaccination are not allowed during the study.

If the participant took a prohibited medication or used a prohibited non-drug therapy for any reason, the investigator should consult with the sponsor to determine if the participant should be withdrawn from study intervention and/or the study.

For the purpose of efficacy analysis, participants receiving any pharmacologically active nonstudy medication or phototherapy for AD will be considered as treatment failures after the start of such medication, except for the use of defined topical rescue medication up to/including Week 8. Whenever possible, efficacy and safety assessments according to Visit 7 (EOT) should be conducted immediately before administering any systemic medications for AD or initiation of phototherapy (= SoC). For zabedosertib, a wash-out period of 7 days (approximately 5 half-lives) is recommended, because there is no experience or data with a combination of zabedosertib and systemic AD treatment.

SoC should be reserved for participants who do not respond adequately to topical treatment (at least 7 days of use). If a participant receives SoC treatment with systemic corticosteroids or non-steroidal systemic immunosuppressive drugs (cyclosporine, methotrexate, MMF, azathioprine, baricitinib etc.) dupilumab, tralokinumab or initiation of phototherapy, study intervention has to be discontinued and EOT assessments including FU visits performed.

7 Discontinuation of Study Intervention and Participant Discontinuation/Withdrawal

Discontinuation of specific sites or of the study as a whole are detailed in Appendix 1 (Section 10.1.11).

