- Sponsor request (after discussion with the investigator), for reasons such as a significant protocol deviation or participant non-compliance.
- Study as whole is terminated by the sponsor.
- Liver safety-related discontinuation criteria are met as described in Section 7.1.1.
- Confirmed creatine kinase (CK) > 10 x ULN or clinical signs of rhabdomyolysis (Section 10.2.1).
- Herpes zoster

A participant should also be permanently discontinued from study intervention for the following **laboratory abnormalities**:

- WBC count < 1000 cells/ μ L; < 1.0 x 10⁹/L
- Absolute neutrophil count < 500 cells/ μ L; $< 0.5 \times 10^9$ /L
- Lymphocyte count < 200 cells/ μ L; < 0.2 x 10⁹/L
- Hemoglobin < 8 g/dL.

Handling of discontinuation of study intervention

For participants who permanently discontinue the study intervention, an EOT visit with all assessments as specified in the SoA (see Section 1.3) should be performed as soon as the study intervention has been discontinued. If the decision to stop the study intervention early is

taken during a site visit, this visit becomes the EOT visit. The FU visit should be performed as planned after the last dose.

After the early EOT visit, treatment with SoC may be started at the discretion of the investigator and entered into the eCRF. For zabedosertib, a wash-out period of 7 days (approximately 5 half-lives) is recommended, because there is no experience or data with a combination of zabedosertib and systemic AD treatment.

See the SoA (Section 1.3) for data to be collected at the EOT and FU and for any further evaluations that need to be completed.

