8.3 Assessment of intercurrent events

Identification of intercurrent event "use of rescue medication"

All medication on the concomitant medication page that is rescue medication according to the protocol and used at or after treatment start will be identified:

- topical corticosteroids (TCS) (Defined rescue medication for this study is the methylprednisolone aceponate (Advantan® cream). Only if Advantan cream is not available in the respective country, an alternative TCS with similar potency may be used (see WHO definition for potent corticosteroids group III, such as betamethasone, fluclorolone, desoximetasone, fluocinolone acetonide, budesonide, mometasone, beclomethasone, hydrocortisone aceponate))
- topical calcineurin inhibitors (TCI) (If TCSs are not tolerated or their use is not advisable, the topical TCIs pimecrolimus 1% (Elidel® cream) or tacrolimus (Protopic® 0.1% or 0.03% ointment) may be used.

Rescue medication will be identified by the following ATC codes if route of administration is topical or cutaneous (in case of multiple possible potency groups for corticosteroids the highest possible potency will be considered):

- Corticosteroids, potent (group III) (D07AC, D07BC, D07CC, D07XC),
- Corticosteroids, very potent (group IV) (D07AD, D07BD, D07CD, D07XD),
- Agents for dermatitis, excluding corticosteroids:
 - Calcineurin-inhibitors Tacrolimus (D11AH01),
 - Calcineurin-inhibitors Pimecrolimus (D11AH02)

The occurrence of the intercurrent event "use of rescue medication" will be applicable if the indication for use of an above listed topical medication is

• "rescue treatment: protocol specified"

or if the indication is

• "treatment of atopic dermatitis related symptoms"

or if the indication is

- "adverse event" and the adverse event is consistent with the indication AD Adverse events will be classified as consistent with AD or not during blind data review by persons without access to any individual post-dose efficacy data. The following AEs will always be considered to be consistant with AD:
 - PT: Dermatitis atopic,
 - PT: Neurodermatitis,
 - PT: Eczema.

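### Protocol 6.9.3's treatment-failure rule for non-study AD drugs is not fully carried into the estimand or SAP 8.3, so a continuing user of an unlisted topical can count as an EASI 75 responder

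*SAP*

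**What the plan says.** Protocol 6.9.3 states an efficacy-analysis rule: "participants receiving any pharmacologically active nonstudy medication or phototherapy for AD will be considered as treatment failures after the start of such medication". It has one exception: "except for the use of defined topical rescue medication up to/including Week 8".

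The composite endpoint in Protocol 3.1 is narrower. Besides EASI 75 and no stop of study drug for lack of efficacy, it asks for "no rescue medication use during the 4 weeks before Day 84 and no use of systemic AD treatment". The estimand (Protocol 3.2, SAP 1.1) has drug-use events only for topical rescue, counted from Day 56 onwards, and for systemic standard of care (SoC).

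SAP 8.3 turns topical rescue into codes: "Rescue medication will be identified by the following ATC codes if route of administration is topical or cutaneous". The codes cover steroid groups III and IV, tacrolimus and pimecrolimus, and the AD-indication test applies only to drugs on that list. This fits the defined rescue of Protocol 6.9.2, where "Only if Advantan cream is not available in the respective country, an alternative TCS with similar potency may be used". The step in SAP 8.4.1 that sets later values to missing uses the same list.

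SAP 6.3 recognises more topical AD drugs with the same indication test: steroid groups I and II, cromoglicic acid (D11AH03), crisaborole (D11AH06) and topical ruxolitinib (D11AH09). It uses them for frequency tables. Protocol 9.3.2.1 and SAP 4.2.2 describe rescue as topical corticosteroids or calcineurin inhibitors, with no potency limit. SAP 4.8 lists two changes to the protocol-planned analyses; this is not one of them.

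**The concern.** For the same participant, two parts of the plan can give opposite values of the primary endpoint. Someone who uses defined rescue on Day 60, as the protocol allows, is a non-responder. Someone who uses topical ruxolitinib for AD on Day 60, which exclusion criterion 9 and Protocol 6.9.3 prohibit, meets no visible rule if study drug continues, although 6.9.3 calls that participant a failure. SAP 8.4.1 itself argues that favourable values after added AD treatment should stay out of the analysis.

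At stake is the responder count in a trial planned with 38 and 19 evaluable participants. The supplementary analyses would not expose the problem. They vary when rescue counts, but rescue is still identified through SAP 8.3.

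**Working it through.** **1. The rules side by side (AD indication assumed)**

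| Case | Protocol 6.9.3 | Estimand and SAP, visible rules |
|---|---|---|
| Systemic SoC or phototherapy | Failure | Non-response |
| Study drug stopped to switch to another AD therapy | Failure | Non-response (counted as lack of efficacy, SAP 8.3) |
| Defined rescue before Day 56 | Exempt | Disregarded |
| Defined rescue on Day 56 (8 × 7 = 56) | Exempt, Week 8 is included | Non-response |
| Defined rescue after Day 56 | Failure | Non-response |
| Crisaborole, cromoglicic acid or topical ruxolitinib, study drug continued | Failure from start | No rule; measured Day 84 EASI stands |
| Group I or II steroid, study drug continued | Failure from start | SAP 4.2.2 wording: non-response from Day 56. SAP 8.3 codes: no rule |

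The rule is therefore partly carried over. Row 6 is a clear gap, row 7 an inconsistency within the SAP, and row 4 a boundary conflict.

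**2. Does anything else make the row 6 user a non-responder?**

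- For prohibited medication, Protocol 6.9.3 says "the investigator should consult with the sponsor to determine if the participant should be withdrawn from study intervention and/or the study". That is case by case. Exclusion 9 names only topical steroids, calcineurin inhibitors and JAK inhibitors, so the step is not clearly triggered for crisaborole or cromoglicic acid.
- Protocol 7.1 allows "Sponsor request (after discussion with the investigator), for reasons such as a significant protocol deviation or participant non-compliance". This too is discretionary.
- The switching reason in SAP 8.3 requires that study drug is stopped.
- The per-protocol validity criterion refers to entry criteria. Exclusion at blind review would remove the participant, which is not the failure that 6.9.3 prescribes.
- The highest-possible-potency rule in SAP 8.3 helps only where a steroid's group is ambiguous.

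**3. Size**

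Inputs: n = 38 and 19, rates 0.49 and 0.16 (Protocol 9.5); Beta(1,1) priors (Protocol 9.3.2.1); acceptance if the posterior probability exceeds 0.90 (Protocol 9.1). Imputation is ignored.

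Posterior = ∫ f(x; k₁+1, 38−k₁+1) · F(x; k₀+1, 19−k₀+1) dx, where f is the Beta density for zabedosertib and F the Beta distribution function for placebo.

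Acceptance probability = Σ Bin(k₁; 38, p₁) · Bin(k₀; 19, p₀) over all (k₁, k₀) with posterior > 0.90.

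*The plan's own figure.* At 0.49 and 0.16 this gives 91.0%, which agrees with the stated at least 90%. With 0.16 in both arms, false acceptance is 6.9%.

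*Near the threshold and away from it:*

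| Zabedosertib | Placebo | Posterior | Accepted |
|---|---|---|---|
| 12/38 | 3/19 | 0.885 | no |
| 13/38 | 3/19 | 0.918 | yes |
| 19/38 | 3/19 | 0.994 | yes |
| 19/38 | 4/19 | 0.981 | yes |
| 19/38 | 5/19 | 0.953 | yes |

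*If exactly one responder is reclassified as 6.9.3 says.* For zabedosertib, sum the probabilities of outcomes accepted at (k₁, k₀) but not at (k₁−1, k₀). For placebo, sum those not accepted at (k₁, k₀) but accepted at (k₁, k₀−1).

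| True rates | Zabedosertib responder: acceptance lost | Placebo responder: acceptance gained |
|---|---|---|
| 0.49 / 0.16 | 3.9% | 5.1% |
| 0.16 / 0.16 | 2.6% | 12.3% |

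*Balanced misclassification.* Five points added in both arms (0.54 / 0.21 and 0.21 / 0.21) moves power from 91.0% to 89.8% and false acceptance from 6.9% to 7.5%. Two extra zabedosertib responders and one extra placebo responder leave power at 91.0% and lower false acceptance to 4.8%.

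*One arm only.* Assume that 2% or 5% of true non-responders are scored as responders. In placebo only (0.16 + 0.05 × 0.84 = 0.202 at 5%), power falls to 88.1% or 83.0%. In zabedosertib only with no true effect, false acceptance rises to 9.3% or 13.8%.

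**The case against.** The strongest case against has four parts.

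- **Much of the rule is carried over.** Systemic SoC, phototherapy, listed rescue from Day 56 and stopping to switch therapy all give non-response. This stands. A reader might infer that the SAP ignores 6.9.3 altogether, and the documents do not support that.
- **Group I and II steroids are covered in words.** Protocol 9.3.2.1 and SAP 4.2.2 set no potency limit. This also stands. For these drugs the fault is that the SAP 8.3 codes are narrower than the SAP's own text.
- **The scenario is narrow.** The participant must use an unlisted topical for AD, stay on study drug and reach EASI 75 at Day 84. Several of these drugs are prohibited, blind review can examine individual cases, and important deviations are tabulated. This limits the likely frequency, but none of it makes such a user a non-responder.
- **The numbers presuppose the event.** The one-responder figures take the reclassified responder as given, in an exploratory Phase 2a trial. The real risk is those figures multiplied by an unknown and possibly very small probability. This is fair, and it limits how serious the point is. It does not remove a contradiction that is cheap to resolve.

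**Conclusion.** The concern holds in a limited form. For a continuing user of crisaborole, cromoglicic acid or topical ruxolitinib for AD, Protocol 6.9.3 says failure and the visible SAP rules allow a responder. For group I and II steroids, SAP 4.2.2 and SAP 8.3 disagree. Rescue on Day 56 itself is exempt in one section and non-response in another. SAP 4.8 declares none of this.

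A reader might go further and infer that the primary result is biased towards zabedosertib. The documents do not support that: they give no frequency of such use, and extra responders could fall in either arm. One reclassified participant matters only near the 90% threshold, balanced misclassification has little effect, and a result such as 19/38 against 3/19 remains accepted with two extra placebo responders. Misclassification confined to one arm would matter more, but nothing in the documents indicates it.

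The conclusion is limited to what can be read. SAP 8.4.2 and 8.4.3 are redacted and figures in 8.4.1 are not shown, so a rule there could narrow the gap. The point should be settled before unblinding, but it does not put the design in question.

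**What to change.** Before unblinding, including that for the interim analysis in SAP 4.7:

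1. Reconcile Protocol 6.9.3 with Protocol 3.1, 3.2 and 9.3.2.1 and with SAP 4.2.2 and 8.3. The result should be one analysis rule that says which AD-active medications count as non-response and from when, including how use on Day 56 itself is treated.
2. If 6.9.3 is to be implemented, add to SAP 8.3 a category for other AD medication. Fill it with the SAP 6.3 topical codes missing from 8.3 (steroid groups I and II, D11AH03, D11AH06, D11AH09) and apply the existing AD-indication test. Classify any other unlisted AD-active drug at blind review. Leave the indication-blind step in SAP 8.4.1 as it is, so that use of the added drugs for other conditions does not erase valid EASI data.
3. If the narrower rule is kept, record it in SAP 4.8 as a departure from 6.9.3 and run the 6.9.3 classification as a sensitivity analysis.
4. Either way, report at blind review the pooled blinded number of participants with an AD topical on the SAP 6.3 list but not on the 8.3 list.

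The cost is SAP wording, one code category, minor programming and a protocol clarification. The downside is that a few responders may become non-responders. This concerns analysis classification only and takes no position on which drugs should be permitted.
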